4.5.5.3 Interim Analyses and Data Monitoring

There are no interim analyses planned for this study.

4.5.5.4 Multicenter Studies

This is a multicenter study with 19 sites participating. Efficacy data collected from all study sites will be pooled for data analysis. The effect of study site on the efficacy analysis results may be explored post-hoc, as needed.

4.5.5.5 Multiple Comparisons/Multiplicity

There will be no adjustments for multiple comparisons in the efficacy analysis for this study. Results are descriptive in nature, and there will be no formal comparisons made between treatment groups.

4.5.5.6 Use of an “Efficacy Subset” of Patients

The primary efficacy analysis will be performed on the Full Analysis Set, and the modified Intent-to-Treat Population will be utilized for sensitivity analyses.

4.5.5.7 Active-Control Studies Intended to Show Equivalence

This study does not include an active-control product and is not intended to demonstrate equivalence between any two drug products.

4.5.5.8 Examination of Subgroups

The primary efficacy endpoint may be summarized by various Phase 2 study patient subgroups of interest based on baseline and demographic categories including age (<65 years of age and \geq 65 years of age), ECOG performance status at study entry (0 and 1), number of prior systemic therapies (1, 2, and 3 lines), gender, and race. Summaries by subgroup will only be produced if there are at least 6 patients in the category of interest. Additional subgroup analyses may be performed post-hoc, as appropriate.

4.5.6 Plasma Concentrations

Plasma concentration measurements will be summarized in a separate report and is outside the scope of this SAP.

4.5.7 Pharmacokinetic Analysis

Pharmacokinetic analysis will be summarized in a separate report and is outside the scope of this SAP.

4.5.8 Pharmacodynamic Analysis

Analysis of selected biomarkers (e.g., plasma EBV DNA levels) will be summarized in a separate report and is outside the scope of this SAP.

4.6 Safety Evaluation

Safety analysis will be carried out for the Safety Analysis Population. Patients who do not complete the study, for whatever reason, will have all available data up until the time of termination included in the analysis. Safety analysis will be summarized by dosing regimen and overall patients combined.

4.6.1 Extent of Exposure

Extent of exposure to nanatinostat, valganciclovir, and pembrolizumab will be summarized for the Safety Analysis Population by dosing regimen. The duration of exposure for each drug will be presented in days and calculated as the date of last dose of study drug minus the date of first dose of study drug, plus one. Duration of exposure and total dose received will be summarized using descriptive statistics. Patients with dosing interruptions greater than 14 days will be flagged in associated patient data listings.

4.6.2 Adverse Events

Treatment-emergent adverse events (TEAEs) are defined as those AEs with onset after the first dose of study drug or existing events that worsened after the first dose during the study. Treatment-emergent AEs will be summarized by phase and treatment group. Events reported with a partial onset date (e.g., month and year are reported but the day

is missing) will be considered to be treatment-emergent if it cannot be confirmed that the event onset was prior to the first dose of study drug based on the available date entries.

Verbatim terms on case report forms will be mapped to preferred terms and system organ classes using MedDRA, version 27.1)

Summaries that are displayed by system organ class and preferred terms will be ordered by descending incidence of system organ class and preferred term within each system organ class. Summaries displayed by preferred term only will be ordered by descending incidence of preferred term. Summaries of the following types will be presented:

- Overall summary of number of unique TEAEs and patient incidence of TEAEs meeting various criteria;
- Overall summary of number of unique treatment-emergent SAEs (TESAEs) and patient incidence of TESAEs meeting various criteria;
- Patient incidence of TEAEs by MedDRA system organ class and preferred term;
- Patient incidence of the most frequently occurring TEAEs (i.e., TEAEs occurring in $\geq 10\%$ of the Safety Analysis Population) by MedDRA preferred term;
- Patient incidence of TEAEs by Common Terminology Criteria for Adverse Events (CTCAE) grade, MedDRA system organ class, and preferred term;
- Patient incidence of TEAEs by relationship to nanatinostat, MedDRA system organ class, and preferred term;
- Patient incidence of TEAEs by relationship to valganciclovir, MedDRA system organ class, and preferred term;
- Patient incidence of TEAEs by relationship to pembrolizumab, MedDRA system organ class, and preferred term;
- Patient incidence of TEAEs related to nanatinostat by CTCAE grade, MedDRA system organ class and preferred term;
- Patient incidence of TEAEs related to valganciclovir by CTCAE grade, MedDRA system organ class and preferred term;
- Patient incidence of TEAEs related to nanatinostat or valganciclovir by CTCAE grade, MedDRA system organ class and preferred term;
- Patient incidence of TEAEs related to pembrolizumab by CTCAE grade, MedDRA system organ class and preferred term;

- Patient incidence of the most frequently occurring TEAEs related to nanatinostat (i.e., related TEAEs occurring in $\geq 10\%$ of the Safety Analysis Population) by MedDRA preferred term;
- Patient incidence of the most frequently occurring TEAEs related to valganciclovir (i.e., related TEAEs occurring in $\geq 10\%$ of the Safety Analysis Population) by MedDRA preferred term;
- Patient incidence of the most frequently occurring TEAEs related to nanatinostat or valganciclovir (i.e., related TEAEs occurring in $\geq 10\%$ of the Safety Analysis Population) by MedDRA preferred term;
- Patient incidence of the most frequently occurring TEAEs related to pembrolizumab (i.e., related TEAEs occurring in $\geq 10\%$ of the Safety Analysis Population) by MedDRA preferred term;
- Patient incidence of TEAEs leading to dosing interruption of nanatinostat by MedDRA system organ class and preferred term;
- Patient incidence of TEAEs leading to dose reduction of nanatinostat by MedDRA system organ class and preferred term;
- Patient incidence of TEAEs leading to dosing interruption of valganciclovir by MedDRA system organ class and preferred term;
- Patient incidence of TEAEs leading to dose reduction of valganciclovir by MedDRA system organ class and preferred term;
- Patient incidence of TEAEs leading to dosing interruption of nanatinostat or valganciclovir by MedDRA system organ class and preferred term;
- Patient incidence of TEAEs leading to dose reduction of nanatinostat or valganciclovir by MedDRA system organ class and preferred term;
- Patient incidence of TEAEs leading to dosing interruption of pembrolizumab by MedDRA system organ class and preferred term;
- Patient incidence of TEAEs leading to dose reduction of pembrolizumab by MedDRA system organ class and preferred term;
- Patient incidence of TEAEs related to nanatinostat leading to discontinuation of study drug by MedDRA system organ class and preferred term;
- Patient incidence of TEAEs related to valganciclovir leading to discontinuation of study drug by MedDRA system organ class and preferred term;
- Patient incidence of TEAEs related to nanatinostat or valganciclovir leading to discontinuation of study drug by MedDRA system organ class and preferred term;

- Patient incidence of TEAEs related to pembrolizumab leading to discontinuation of study drug by MedDRA system organ class and preferred term;
- Patient incidence of SAEs by MedDRA system organ class and preferred term;
- Patient incidence of SAEs by CTCAE grade, MedDRA system organ class and preferred term;
- Patient incidence of SARs (nanatinostat) by MedDRA system organ class and preferred term;
- Patient incidence of SARs (valganciclovir) by MedDRA system organ class and preferred term;
- Patient incidence of SARs (nanatinostat or valganciclovir) by MedDRA system organ class and preferred term;
- Patient incidence of SARs (pembrolizumab) by MedDRA system organ class and preferred term;
- Patient incidence of dose-limiting toxicities by MedDRA system organ class and preferred term;
- Patient incidence of TEAEs leading to death by MedDRA system organ class and preferred term.

Selected AE summaries may also be repeated for different age subgroups (<65 years old, \geq 65 years old) if there are at least 5 patients enrolled in each age group.

At each level of summarization (e.g., any AE, system organ class, and preferred term), patients experiencing more than one TEAE will be counted only once. In the summary of TEAEs by severity grade, patients will be counted once at the highest severity reported at each level of summarization; in the summary of TEAEs by relationship, patients will be counted once at the closest relationship to study drug. Related events include those reported as “Possibly Related” or “Definitely Related” to each study drug; events considered not related are those reported as “Not Related” to each study drug.

For summaries of treatment-related TEAEs by CTCAE grade, a column summarizing patients with at least one treatment-related Grade ≥ 3 TEAE will also be presented.

Adverse event data will be presented in data listings by patient, treatment regimen, and event. Serious AEs and AEs leading to permanent discontinuation of the study drugs will also be presented in separate data listings.

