7.4.2. Safety and Tolerability Assessments

Study assessments of safety include AEs, clinical laboratory tests, ECGs, vital signs, physical examinations, and ECOG status.

Safety data will be collected from the signing of the ICF up to and including 90 days post-last dose of study treatment according to the Schedule of Events in Table 11.

Adverse event monitoring and collection, in addition to other safety considerations, are summarized in Section 8. Laboratory assessments, vital signs, ECGs, physical examinations, and ECOG performance status are described in the subsequent sections below.

Tolerability will be assessed by the incidence of AEs leading to dose modifications or study drug discontinuation.

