9.7. Safety Analysis

Safety analysis will be based on all patients in the Safety population and will be summarized overall, by dosing regimen, and by any other relevant subgroup (eg, solid tumor type).

Study medication exposure will be summarized for each patient and tabulated by dosing regimen including duration of study medication, total dose taken, and dose reductions.

Adverse events, vital sign measurements, clinical laboratory measurements, and concomitant medications will be summarized overall and by dosing regimen. Tabulations and listings of values for dose holds, modifications, or discontinuations; vital signs; and laboratory safety evaluations will be presented.

Adverse events will be coded according to MedDRA and classified using the NCI CTCAE v5.0. The incidence rates of AEs will be tabulated by System Organ Class and Preferred Term. Subsets of AEs to be summarized include SAEs, events of all CTCAE grade severities, suspected

treatment-related AEs, and events that resulted in withdrawal of study medication. The most severe grade of each preferred term for a patient will be utilized for summaries of AEs by NCI CTCAE grade. All AEs with corresponding attributes will be displayed in a by-patient listing. Adverse events leading to death or to discontinuation from treatment, events classified as NCI CTCAE Grade 3 or higher, suspected treatment-related events, all deaths, and SAEs will also be displayed in by-patient listings separately.

Clinical laboratory results will be summarized descriptively by dosing regimen, which will also include a display of change from baseline. Laboratory values outside of the normal ranges will be identified. Clinically significant hematologic and non-hematologic laboratory abnormalities that meet Grade 3 or Grade 4 criteria according to the CTCAE will be listed and summarized. Graphical display of selective lab parameters over the course of study will be provided.

Vital sign measurements will be listed for each patient at each visit. Descriptive statistics for vital signs, both observed values and changes from baseline, will be summarized by dosing regimen.

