4.8 Changes in the Conduct of the Study or Planned Analyses

Enrollment into Study VT3996-301 was discontinued after completion of the final Phase 1b dose level for business reasons unrelated to clinical factors or safety concerns. Patients who were receiving study drugs at the time of the study discontinuation notice continued to remain on study treatment as long as they derived clinical benefit, and they were to remain on study including and up to their final Safety Follow-Up Visit. Patients who were in the Long-Term Follow-Up period transitioned to End of Study. Reporting of serious adverse events continued per clinical study protocol Section 8.2.1.

Consequently, study conduct did not proceed to Phase 2 after the recommended Phase 2 dose of nanatinostat and valganciclovir was determined, and thus the Phase 2 study-specific analyses described in this SAP will not be performed. The study will be considered complete when all patients have completed safety follow-up assessments.

The only changes to the study conduct or planned analyses identified within the development of this SAP relative to the descriptions provided within the clinical study protocol are described below:

- Section 2 of the clinical study protocol only specified ORR as a primary efficacy endpoint for Phase 2, while ORR was added as a primary efficacy endpoint for Phase 1b in this SAP.
- Section 9.1 of the clinical study protocol states that all data will be summarized by dosing regimen, disease subtype, and overall, but data summaries by disease subtype are unnecessary since Phase 1b only enrolled patients with RM-NPC, and the study did not proceed to Phase 2.

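### SAP 4.6.2 tabulates TEAEs leading to discontinuation by event term only when judged drug-related, although the protocol's tolerability measure has no relatedness limit

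*SAP*

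**What the plan says.** Protocol 7.4.2 defines the measure: "Tolerability will be assessed by the incidence of AEs leading to dose modifications or study drug discontinuation". It carries no relatedness qualifier. Protocol 9.7 lists the subsets of adverse events to be summarised, and its list ends with "treatment-related AEs, and events that resulted in withdrawal of study medication". Relatedness and withdrawal are two separate entries.

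SAP 4.6.2 names eight tables for interruptions and reductions: two actions, each for nanatinostat, valganciclovir, either of the two, and pembrolizumab. None is restricted by relationship; one reads "Patient incidence of TEAEs leading to dosing interruption of nanatinostat by MedDRA system organ class and preferred term". It then names four tables for discontinuation, all restricted. The first is specified as "Patient incidence of TEAEs related to nanatinostat leading to discontinuation of study drug by MedDRA system organ class and preferred term". The other three apply the same limit, with valganciclovir, either of those two drugs, or pembrolizumab as the drug held responsible.

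SAP 1 says that changes from the protocol's statistical methods will be explained in the SAP. SAP 4.8 opens its list with "The only changes to the study conduct or planned analyses identified within the development of this SAP" and gives two items: ORR added as a Phase 1b primary efficacy endpoint, and summaries by disease subtype dropped. Neither concerns discontinuation.

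**The concern.** Discontinuation is the most serious of the three dosing consequences, and it is the only one for which the SAP names no all-cause table by system organ class and preferred term. The restriction rests on the investigator's causality judgement (Protocol 8.4) in an open-label study (Protocol 5.8.3). Safety and tolerability is a secondary objective.

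The tables also differ in what they index. Interruptions and reductions are classified by the drug whose dosing was changed. Discontinuations are classified by the drug held responsible, with the drug stopped given only as study drug. The two groups therefore cannot be read together as one account of tolerability by drug. What is at stake is whether the Phase 1b report shows the measure that the protocol describes.

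**Working it through.** The plan gives no discontinuation rate, so there is no figure to reproduce. The check compares texts and then asks which way the difference can go.

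**1. Does the protocol ask for an all-cause summary?** Protocol 7.4.2 has no relatedness limit. Protocol 9.7 lists treatment-related events and events leading to withdrawal as separate subsets. A withdrawal summary limited to related events would answer neither text.

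**2. Does the SAP commit to one?**

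| Outcome | Location in SAP | Limited to related events? | Gives incidence by event term? |
|---|---|---|---|
| Interruption (4 tables) | 4.6.2 | No | Yes |
| Reduction (4 tables) | 4.6.2 | No | Yes |
| Discontinuation (4 tables) | 4.6.2 | Yes, all four | Yes |
| Events leading to discontinuation or withdrawal | 4.6.2 and 4.6.3 listings | No | No, by-patient listing |
| Treatment discontinuation by primary reason | 4.3.1 disposition | No | No, reason only |
| TEAEs meeting unspecified criteria | 4.6.2 overall summary | Not stated | No |

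No row gives all-cause discontinuation by event term. The disposition table comes nearest to an all-cause rate, but it records only the primary reason and names no event.

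**3. Direction.** Let N be the patients in a dosing regimen, A those with any TEAE leading to discontinuation, and R those with at least one such TEAE judged related. R is a subset of A, so R/N ≤ A/N. With s = R/A, the gap is (A/N) × (1 − s). It is zero only when every patient who stops for an adverse event has at least one such event judged related.

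**4. Effect of one patient.** SAP 4.1.1 summarises by dosing regimen, and the protocol plans cohorts of 3 to 6. One patient whose only discontinuing event is judged unrelated counts as 0 in the related-only table and as 1 in the all-cause table:

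- N = 3: 1/3 = 33% against 0%.
- N = 6: 1/6 = 17% against 0%.

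The difference is smaller where a regimen has more than 6 patients.

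**5. Overall illustration.** These inputs are assumptions; none is in the documents. Take an all-cause rate of 10% to 20% and s of 25% to 75%.

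- Smallest gap: 10% × (1 − 0.75) = 2.5 points.
- Largest gap: 20% × (1 − 0.25) = 15 points.

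**The case against.** The strongest reply is that little is hidden.

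- **The tables are labelled as related-only.** A correctly titled subset is not a biased estimate. This stands. Understatement arises only if those tables are presented as the tolerability measure, so a reader who infers that the rate will necessarily be understated goes too far.
- **All-cause information exists elsewhere.** This also stands. A reader might infer that all-cause discontinuations are tabulated nowhere, but SAP 4.3.1 tabulates treatment discontinuation by primary reason with no relatedness limit, and Protocol 7.3.3 lists adverse event among the withdrawal reasons. The overall TEAE summary may contain an all-cause row. What remains missing is a committed incidence by event term, which the SAP does give for the lesser dosing actions.
- **Related is defined broadly.** Under Protocol 8.4, an unrelated event needs both timing that makes causation very unlikely and a reasonable alternative explanation, and SAP 4.6.2 counts possibly related events as related. The gap may therefore be small. Without the all-cause table, its size cannot be read from any committed summary.
- **Small cohorts make such tables sparse.** True, but the SAP accepts that for interruptions and reductions.

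A reader might also infer harm to the choice of RP2D. The documents do not support this. SAP 4.8 states that the study stopped before Phase 2, after the RP2D had been determined, so these final tables cannot inform that decision. For the same reason the pembrolizumab tables have no content.

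**Conclusion.** The point holds as a mismatch between protocol and SAP in Phase 1b safety reporting. The protocol's tolerability measure and its planned withdrawal summary are all-cause. The SAP commits to event-term tables for related discontinuations only, departs from its own practice for interruptions and reductions, and does not declare the change.

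The direction is certain: a related-only rate cannot exceed the all-cause rate. The size is unknown. The 17 to 33 points per patient follow from the planned cohort sizes, and the 2.5 to 15 points rest wholly on assumed rates. The conclusion also assumes that the unnamed criteria of the overall TEAE summary cannot be counted as a commitment. Even if they include all-cause discontinuation, the breakdown by event term would still be missing. The matter is worth correcting before reporting, but it does not threaten the validity of the study.

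**What to change.** In SAP 4.6.2:

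1. Add three tables giving the patient incidence of TEAEs, regardless of relationship, that led to discontinuation of nanatinostat, of valganciclovir, and of either, by system organ class, preferred term and dosing regimen. Use these for tolerability.
2. Name the criteria of the overall TEAE summary and include an all-cause discontinuation row.
3. Keep the related-only tables, presented as subsets of the new ones.

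No pembrolizumab version is needed. If the sponsor prefers not to add the tables, SAP 4.8 should declare the departure from Protocol 7.4.2 and 9.7 and give the reason.

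The cost is about three tables. SAP 4.6.3 already plans listings of events that led to withdrawal of each study drug, so no new data should be needed. The stated discontinuation rate may be less favourable.

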5.5. Dose Escalation Guidelines

5.5.1. Provisional Dose Levels

Table 4 describes the starting doses and the provisional dose levels of nanatinostat and valganciclovir (Phase 1b) and nanatinostat and valganciclovir with pembrolizumab (Phase 2 Dose Optimization and Phase 2 Expansion) to be evaluated. The actual dose levels will be determined based on available data following a discussion with Investigators during dose-escalation teleconferences. No intrapatient dose escalation will be permitted in the Phase 1b dose escalation.

Table 4: Phase 1b: Dose Levels – Nanatinostat and Valganciclovir

Dose Level	Nanatinostat Oral Dose on Days 1-4/Week	Valganciclovir Oral Dose Daily
-1	10 mg once daily	900 mg once daily
1	20 mg once daily	900 mg once daily
2	30 mg once daily	900 mg once daily
3	40 mg once daily	900 mg once daily
4	20 mg and 10 mg divided dose	900 mg once daily
5	20 mg twice daily	900 mg once daily
6	10 mg twice daily	900 mg twice daily × 21 days, then once daily
7	20 mg and 10 mg divided dose	900 mg twice daily × 21 days, then once daily
	Nanatinostat Oral Dose Twice Daily on Days 1-7/Week	Valganciclovir Oral Dose Twice Daily on Days 1-7/Week
8 ^a	20 mg and 10 mg divided dose	450 mg twice daily

9ª	20 mg and 20 mg divided dose 450 mg twice daily			
10 ^a	30 mg and 20 mg divided dose	450 mg twice daily		
11ª	30 mg and 30 mg divided dose	450 mg twice daily		
12ª	40 mg and 30 mg divided dose	450 mg twice daily		
13ª	40 mg and 40 mg divided dose	450 mg twice daily		

DLT = dose-limiting toxicity; RP2D = recommended Phase 2 dose

Guidelines for Dose Escalation 5.5.2.

During the DLT evaluation window of both phases of the study, patients who permanently discontinue study treatment prior to receiving 75% of the planned number of nanatinostat and valganciclovir doses or 2 pembrolizumab doses due to reasons other than study drug-related toxicity will not be considered evaluable for DLT and may be replaced.

Phase 1b

IND 154400

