9.3. Definition of Analysis Populations

The following patient populations will be assessed:

- 1. **Safety Analysis population:** All patients who receive at least one dose of study treatment (nanatinostat, valganciclovir, or pembrolizumab). The safety analysis population will be used for all listings and all demographic and baseline summaries.
- 2. **Full Analysis Set:** All patients with measurable disease at baseline who receive at least one dose of nanatinostat and valganciclovir with or without pembrolizumab and who have at least one post-baseline tumor assessment. Patients will be analyzed according to the dosing regimen for which they have been assigned. The full analysis set will be used for summaries of tumor response and survival metrics.
- 3. **Modified Intent-to-Treat (mITT) population:** The mITT population is defined as all RM-NPC patients who have received at least one dose of study treatment (nanatinostat,

valganciclovir, or pembrolizumab), have a confirmed diagnosis of EBV⁺ by central pathology review, met all inclusion criteria, and have baseline (screening) and at least one post-baseline tumor assessment for efficacy.

4. **PK population:** All treated patients with at least one available PK parameter of interest.

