4.1.1 Reporting Conventions

The Phase 1b and Phase 2 portions of the study will be analyzed separately. Tables and figures will be summarized by dosing regimen. In general, all data collected, and any derived data will be presented in patient data listings, for all enrolled patients. Listings will be ordered by phase, site, patient number, treatment regimen, and assessment or event date. The dosing regimen presented in listings will be based on the planned assignment, unless otherwise noted.

In general, continuous variables will be summarized to indicate the study population sample size (N), number of patients with available data (n), mean, SD, median, first (Q1) and third (Q3) quartiles, minimum, and maximum values. Categorical variables will be summarized by the population size (N), number of patients with available data (n), number of patients in each category, and the percentage of patients in each category. Unless otherwise noted, and in order to determine the percentage of patients in each category, the denominator will be based on the number of patients with available data.

Select ordinal data may be summarized using both descriptive statistics and counts and percentages of patients in each category, as appropriate.

Non-zero percentages will be rounded to one decimal place. Rounding conventions for presentation of summary statistics will be based on the precision of the variable of summarization, as it is collected in its rawest form (i.e., on the electronic case report form [eCRF] or as provided within an external file) and are outlined as follows:

- The mean and median will be rounded to one more decimal place than the precision of the variable of summarization;
- Measures of variability (e.g., standard deviation, standard error) will be rounded to two more decimal places than the precision of the variable of summarization; and
- Minimum and maximum values will be presented using the same precision as the variable of summarization.

Other statistics (e.g., CIs) will be presented using the same general rules outlined above or assessed for the most appropriate presentation based on the underlying data.

No formal statistical analysis will be performed to compare treatment regimens. This study is exploratory in nature; descriptive statistics will be tabulated by treatment regimen and reviewed to evaluate all study endpoints.

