4.2 Analysis Sets

The analysis sets are defined as follows:

- Safety Analysis Population: Includes all patients who receive at least one dose of study treatment (nanatinostat, valganciclovir, or pembrolizumab). The Safety Analysis Population will be used for all summaries of safety, demographic, and baseline summaries.
- Full Analysis Set: Includes all patients with measurable disease at baseline who receive at least one dose of nanatinostat and valganciclovir with or without pembrolizumab and who have at least one post-baseline tumor assessment. Patients will be analyzed according to the dosing regimen for which they have been assigned. The Full Analysis Set will be used for summaries of tumor response and survival metrics.

Modified Intent-to-Treat Population: Includes all RM-NPC patients who receive at least one dose of study treatment (nanatinostat, valganciclovir, or pembrolizumab), have a confirmed diagnosis of EBV^+ by central pathology review, met all eligibility criteria, and have baseline (screening) and at least one post-baseline tumor assessment for efficacy.

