4.5.2 Measurements of Treatment Compliance

Compliance with both nanatinostat and valganciclovir will be determined as the total number of tablets taken divided by the expected number of tablets taken, multiplied by 100.

The expected number of tablets administered will be determined using the prescribed dosing information contained in Table 4 of the clinical study protocol, where nanatinostat and valganciclovir are dispensed in 10 mg and 450 mg tablets, respectively. The number of tablets expected will be calculated for each cycle and then multiplied by the number of cycles the patient completes.

The total number of tablets taken will be determined using the data recorded on the Study Drug Exposure eCRF pages for nanatinostat and valganciclovir. If a patient is administered study drug as expected (with no changes to dose administered, no interruptions, delays, or missed doses), then the Study Drug Exposure eCRFs will include a record for that cycle that indicates “No Change to Dose.” In this case, the total number of tablets taken in each cycle will be calculated as the number of days in the cycle where the doses were administered (multiplied by two if a divided dose). Missed doses are recorded on the Study Drug Exposure eCRFs as “Missed/Dosing Error.” When calculating the number of missed doses, if a patient reports “Missed/Dosing Error” on the eCRF, it will be assumed no study drug was administered on that date.

Compliance with pembrolizumab will be determined as the total number of infusions received divided by the number of expected infusions, multiplied by 100. The number of expected infusions will be determined using the dosing schedule provided in Figure 10 of the clinical study protocol. The total number of infusions received will be determined using the *Study Drug Administration Log - Pembrolizumab* eCRF.

Dosing compliance will be summarized using descriptive statistics, for each dosing regimen based on the Safety Analysis Population. The number and percentages of patients who are <80% compliant and $\geq 80\%$ compliant within each dosing regimen will be summarized. Treatment compliance will also be included in a by-patient data listing.

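### Phase 1b DLT incidence is reported on all treated patients, although Protocol 5.5.2 makes some of them not evaluable for DLT and no DLT-evaluable set is defined

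*SAP*

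**What the plan says.** Protocol Section 2 (Table 3) makes DLT incidence during the evaluation period the Phase 1b primary endpoint, and Protocol 5.5.3.1 sets that period at 28 days.

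Protocol 5.5.2 says who counts. Patients who stop permanently "prior to receiving 75% of the planned number of nanatinostat and valganciclovir doses" and do so "due to reasons other than study drug-related toxicity will not be considered evaluable for DLT and may be replaced". (The alternative condition on pembrolizumab doses does not arise in Phase 1b.)

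The SAP's DLT output is a single item in the adverse event list of 4.6.2: "Patient incidence of dose-limiting toxicities by MedDRA system organ class and preferred term". It states no population, evaluability rule or time window. Two general statements then govern it:

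- SAP 4.2: "The Safety Analysis Population will be used for all summaries of safety, demographic, and baseline summaries". That population is everyone with at least one dose of any study drug.
- SAP 4.6: "Safety analysis will be carried out for the Safety Analysis Population".

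SAP 4.2 otherwise defines only the Full Analysis Set and the modified Intent-to-Treat Population. Protocol 9.3, under "The following patient populations will be assessed", adds only a PK population.

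**The concern.** The population that the SAP assigns to the DLT table is wider than the one the protocol calls evaluable. A patient who took a few doses and left for an unrelated reason has not been observed long enough to count as free of DLT, which is why the protocol allows replacement. In the all-treated denominator that patient counts as a patient without a DLT, and the reported rate falls below the one that 5.5.2 implies.

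Nothing else in the plan fills the gap. Protocol Table 3 refers the reader to Section 9.6.1 for the analysis of primary endpoints, but 9.6.1 covers only ORR. SAP 4.8 lists the changes from the protocol and does not mention the DLT denominator. It also says that the study did not proceed to Phase 2, so the Phase 1b table is the only DLT result the study will report.

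**Working it through.** **1. Which denominator applies.** The default in SAP 4.1.1 is that "the denominator will be based on the number of patients with available data". It does not carry the 75% rule, and the SAP does not say when a patient has available DLT data. The two population statements in 4.2 and 4.6 remain, and both lead to all treated patients.

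**2. The protocol's own figure.** Protocol 5.5.2 sets the RP2D criterion at fewer than 33% of patients with a DLT, and Table 5 accepts 1 of 6 and rejects 2 or more of 6. These agree: 1/6 = 16.7% is below 33%, and 2/6 = 33.3% is not.

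**3. Effect on the reported rate.** Let x be patients with a DLT, n evaluable patients, and k treated but non-evaluable patients without a DLT. The protocol's rate is x/n; the SAP's is x/(n + k). The documents do not give k. If each non-evaluable patient is replaced:

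| Evaluable (x/n) | k = 1 | k = 2 |
|---|---|---|
| 2/6 = 33.3% | 2/7 = 28.6% | 2/8 = 25.0% |
| 1/6 = 16.7% | 1/7 = 14.3% | 1/8 = 12.5% |
| 2/3 = 66.7% | 2/4 = 50.0% | – |
| 0/3 = 0% | 0/4 = 0% | – |

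Without replacement the direction is the same: 2/5 = 40.0% becomes 2/6 = 33.3%.

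**4. A narrow case in the other direction.** A patient may have a DLT and then stop before 75% of doses for an unrelated reason. The literal wording of 5.5.2 excludes this patient; the Safety Analysis Population counts them. With six treated, two DLTs and one such patient, all-treated gives 2/6 = 33.3% and the literal rule gives 1/5 = 20.0%. The case is narrow because stopping for treatment-related toxicity is itself a DLT under 5.5.3.1.

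**5. Can a reader rebuild the evaluable count?** Not reliably.

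- Cohort size does not reveal it. Protocol 3.1 lets patients already in screening join a full cohort, so seven treated may be seven evaluable, or six evaluable and one replaced.
- The compliance measure in SAP 4.5.2 does not help: "The number of tablets expected will be calculated for each cycle and then multiplied by the number of cycles the patient completes". A patient who stops within Cycle 1 has completed no cycle, so the expected count is zero.

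**6. Is the 75% rule clear enough to program?** It does not say whether both drugs must reach 75% or either one. Planned doses over 28 days follow from Protocol Table 4. Assuming no earlier missed doses and all doses taken on the last day:

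| Dose levels | Nanatinostat doses | Valganciclovir doses | Nanatinostat reaches 75% | Valganciclovir reaches 75% |
|---|---|---|---|---|
| 1–3 | 4 × 4 = 16 | 28 | Day 18 (12/16) | Day 21 (21/28) |
| 4–5 | 2 × 16 = 32 | 28 | Day 18 (24/32) | Day 21 (21/28) |
| 6–7 | 2 × 16 = 32 | 2 × 21 + 7 = 49 | Day 18 (24/32) | Day 19 (38/49) |
| 8–13 | 2 × 28 = 56 | 2 × 28 = 56 | Day 21 (42/56) | Day 21 (42/56) |

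At levels 1–5, a last dose on Day 18, 19 or 20 leaves nanatinostat at 75.0% but valganciclovir at 18/28 = 64.3%, 19/28 = 67.9% or 20/28 = 71.4%. At levels 6–7 the readings differ only on Day 18 (24/32 = 75.0% against 36/49 = 73.5%). At levels 8–13 they agree.

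**The case against.** The strongest reply is that no effect has been shown. The documents do not say that any patient was non-evaluable, reporting is descriptive, and Table 5 acts on counts in consultation with the SMC, not on a printed percentage. SAP 4.8 also says that the RP2D was already determined. All of this stands, and it limits the point to reporting. The shift is also small beside the sampling uncertainty: the exact 95% interval is 4.3% to 77.7% for 2/6 and 3.7% to 71.0% for 2/7.

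A second reply is that the SAP follows the protocol. Protocol 9.7 bases safety analysis on the Safety population, Protocol 9.3 lists no DLT set, and the 75% rule sits among the escalation guidelines. This is fair as to origin: the gap is shared by both documents. It does not remove the conflict between 5.5.2, which says who is evaluable for DLT, and a primary-endpoint table that ignores it.

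A third reply is that discontinuation reasons and exposure will be reported, so evaluability could be worked out by hand in cohorts this small. A reader could try, but no flag or table gives the answer, and at levels 1–7 it can depend on an unstated reading of the rule.

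Finally, evaluability decided during escalation may not be recorded in the database, and may differ from a later derivation. That is a fair caution, and the fix allows for it.

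**Conclusion.** The concern holds. As written, the SAP puts the protocol's Phase 1b primary endpoint on all treated patients, a group that can include patients whom Protocol 5.5.2 calls not evaluable for DLT, and no document defines the evaluable set.

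The size depends on an unknown number of non-evaluable patients. One such patient without a DLT, added to six evaluable, lowers a two-DLT rate by 33.3 − 28.6 = 4.7 percentage points from the rounded figures. In that example a level that failed the under-33% criterion would be printed with a rate that appears to meet it. With no non-evaluable patients, or no DLT at the level, the rate does not change. The number of patients with a DLT stays visible throughout.

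This should be corrected before reporting, but it does not call the dose decisions into question.

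**What to change.** - Add a DLT-evaluable set to SAP 4.2 that applies Protocol 5.5.2 as it was applied during escalation. State whether 75% had to be reached for both drugs or for either, and how a patient with a DLT who later stopped for an unrelated reason was classified.
- Report, by dose level, patients with at least one DLT in the 28-day window over DLT-evaluable patients, as n/N.
- List treated patients who were not evaluable, with the reason.
- Keep the table by system organ class and preferred term on the Safety Analysis Population, labelled as supportive.

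The cost is one definition, one table, one short listing and one small derivation: the percentage of planned Cycle 1 doses taken, per drug, from the Study Drug Exposure eCRF. SAP 4.5.2 treats any date with a missed dose or dosing error as a day without drug, so the percentage is approximate for divided doses. It should be checked against the record of the escalation decisions where one exists. No new data collection is needed. If every treated patient was evaluable, one sentence saying so closes the point.
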